2.3.2 Secondary endpoints

- 2.3.2.1 Number of readmission/ ER visit that is hypertension related
- **2.3.2.2** Frequency of severe hypertension (SBP>160mmHg or DBP>110mmHg)
- **2.3.2.3** Number of days required until blood pressure resolution (<140/90 for 2 days)
- 2.3.2.4 Postpartum length of stay
- 2.3.2.5 Complications during hospitalization related to hypertensive disorders of pregnancy (acute pulmonary edema, acute kidney injury, disseminated intravascular coagulation, stroke or myocardial infarction, eclampsia, ICU stay, maternal death)
- **2.3.2.6** Adverse effects secondary to furosemide

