4.7 Management of blinding

This is a double blind study and therefore physicians, staff, and patients will be blinded to the patient's allocated treatment group. In the event of a potential suspected unexpected serious adverse reaction, unblinding will be undertaken by the PI. Unblinding may also be performed at the request of a senior clinician responsible for the care of a trial participant but such requests are likely to occur only in the case of an adverse clinical event and are expected to be rare. Any request to unblind treatment allocation for clinical reasons will be made directly to IDS and the treatment allocation will be reported to the relevant clinician. The PI and main trial manager will be kept informed of all instances of unblinding but remain blind to treatment allocations themselves wherever possible. All requests for unblinding will be recorded by research staff and IDS.

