7 ADVERSE EVENTS

7.1 Adverse Event Monitoring

Adverse event data collection and reporting will be done to ensure the safety of subjects who will enroll be enrolled in thus study. Adverse events will be reported in a routine manner at scheduled times during the trial. Additionally, certain adverse events will be reported in an expedited manner to allow for optimal monitoring of patient safety and care.

All patients experiencing an adverse event, regardless of its relationship to study drug/device, will be monitored until:

- the adverse event resolves or the symptoms or signs that constitute the adverse event return to baseline;
- > any abnormal laboratory values have returned to baseline;
- there is a satisfactory explanation other than the study drug for the changes observed; or
- death.

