7.2 Definitions

7.2.1 Definition of Adverse Event

An adverse event (AE) is any untoward medical occurrence in a patient receiving study treatment and which does not necessarily have a causal relationship with this treatment. An AE can therefore be any unfavorable and unintended sign (including an abnormal laboratory finding), symptom, or disease temporally associated with the use of an experimental intervention, whether or not related to the intervention.

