7.3 Steps to Determine If an Adverse Event Requires Expedited Reporting

Step 1: Identify the type of adverse event

Step 2: Grade the adverse event

Step 3: Determine whether the adverse event is related to the protocol therapy Attribution categories are as follows:

- Definite The AE is clearly related to the study treatment.
- Probable The AE is likely related to the study treatment.
- Possible The AE *may be related* to the study treatment.
- Unrelated The AE is clearly NOT related to the study treatment.

Step 4: Determine the prior experience of the adverse event.

Expected events are those that have been previously identified as resulting from administration of the agent. An adverse event is considered unexpected, for expedited reporting purposes only, when either the type of event or the severity of the event is not listed in:

- the current known adverse events listed in the Agent Information Section of this protocol;
- the drug package insert;
- · the current Investigator's Brochure

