7.4 Reporting Requirements for Adverse Events

7.4.1 Expedited Reporting

- The Principal Investigator will be notified within 24 hours of learning of any serious adverse events, regardless of attribution, occurring during the study or within 30 days of the last administration of the study drug.
- The University of Pennsylvania IRB must be notified within 10 business days of "any unanticipated problems involving risk to subjects or others" (UPR/UPIRSO).

The following events meet the definition of UPR:

- Any serious event (injuries, side effects, deaths or other problems), which in the opinion of the Principal Investigator was unanticipated, involved risk to subjects or others, and was possibly related to the research procedures.
- Any serious accidental or unintentional change to the IRB-approved protocol that alters the level of risk.
- 3. Any deviation from the protocol taken without prior IRB review to eliminate apparent immediate hazard to a research subject.
- 4. Any new information (e.g., publication, safety monitoring report, updated sponsor safety report), interim result or other finding that indicates an unexpected change to the risk/benefit ratio for the research.
- 5. Any breach in confidentiality that may involve risk to the subject or others.
- 6. Any complaint of a subject that indicates an unanticipated risk or that cannot be resolved by the Principal Investigator.

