8 DRUG/DEVICE INFORMATION

8.1 Furosemide

- Other names for the drug: Lasix
- Classification type of agent: Loop diuretic; Antihypertensive
- Mode of action: inhibits reabsorption of sodium and chloride in the ascending loop of Henle and distal renal tubule, interfering with the chloride-binding co-transport system, thus causing increased excretion of water, sodium, chloride, magnesium, and calcium
- Protocol dose: 20 mg, daily
- Route of administration for this study: Oral
- Incompatibilities: NSAIDs may diminish the diuretic effect of loop diuretics. Loop diuretics may enhance the nephrotoxic effect of NSAIDs. Monitoring for evidence of kidney injury or decreased therapeutic effects of loop diuretics with concurrent use of an NSAID.
- Availability: commercially available, on formulary
- Side effects: ototoxicity, mood changes, confusion, muscle pain, palpitations, dizziness, syncope, increased thirst, fatigue, weakness, decreased appetite, dry mouth, dry eyes, upset stomach, nausea, and emesis associated with fluid and electrolyte problems (Please refer to the manufacturer's package insert for a complete list of adverse events)
- Nursing implications: PO administration should be on empty stomach

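### Safety endpoint 2.3.2.6 is worded by cause and left undefined, and the plan does not commit to comparing adverse events by arm regardless of attribution

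*Combined protocol and SAP*

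**What the plan says.** Section 2.3.2 gives the safety endpoint as "Adverse effects secondary to furosemide" and adds nothing about which events qualify, who decides, over what period, or how events are counted in the placebo arm.

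Elsewhere the protocol is neutral about cause:

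- Section 7.2.1 defines an adverse event as an occurrence "which does not necessarily have a causal relationship with this treatment".
- Section 7.1 provides that "All patients experiencing an adverse event, regardless of its relationship to study drug/device, will be monitored until" resolution or one of its other end points.
- Section 7.4.1 requires notification of "any serious adverse events, regardless of attribution, occurring during the study" or within 30 days of the last dose.

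Section 7.3 contains a causality step, "Determine whether the adverse event is related to the protocol therapy", with four grades from definite to unrelated. It belongs to the procedure for deciding on expedited reporting.

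Section 8.1 lists known effects, among them "ototoxicity, mood changes, confusion, muscle pain, palpitations, dizziness, syncope, increased thirst, fatigue, weakness". Section 4.2 names ototoxicity and symptomatic electrolyte disturbance as the toxicities to be assessed.

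Under Section 4.7, "physicians, staff, and patients will be blinded to the patient's allocated treatment group". The safety/tolerability note under Section 6.1 sets the safety population as everyone who took at least one dose, but does not name the events to be analysed. Section 9.2 gives generic between-group tests and relative risks with 95% confidence intervals, and mentions no safety outcome.

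**The concern.** An endpoint worded by cause sits badly in a blinded randomised trial. No event in a placebo recipient can literally be due to study furosemide, and nobody assessing events knows who is on placebo. Applied as written, the endpoint asks staff to guess cause case by case. Many of the listed effects (fatigue, weakness, dizziness, mood changes) have ready alternative explanations in the days after delivery, so such guesses carry little information. Comparing the arms on all events needs no guess, because randomisation supplies the attribution.

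Two things are at stake. First, two teams could read 2.3.2.6 differently and report different counts from the same data. Second, under the literal reading, part of any real excess on furosemide could be left out of the compared counts, which weakens the trial's ability to describe harm. No other provision makes up for this by promising a table of all adverse events by arm.

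**Working it through.** The plan states no adverse-event rate and no power for this endpoint, so there is no figure to reproduce. The check has two parts.

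**1. The sections side by side**

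| Question | What the documents provide |
|---|---|
| Which events count for 2.3.2.6? | Not stated. Lists of known effects exist in 1.2, 4.2 and 8.1, but the endpoint does not point to them |
| Who judges cause, and at what level? | Not stated for the endpoint. The 7.3 grades serve expedited reporting |
| Over what period? | Not stated for the endpoint. 7.4.1 gives 30 days after the last dose for serious events only |
| In whom? | Everyone with at least one dose (safety/tolerability note under 6.1) |
| Are events defined and followed regardless of cause? | Yes (7.1, 7.2.1; serious events also 7.4.1) |
| Are all events compared by arm? | No section says so |

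Two readings of 2.3.2.6 are therefore open: (a) events judged to be caused by the drug; (b) known furosemide effects, counted in both arms. Only reading (a) involves a filter.

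**2. What a filter would do under reading (a): illustration with assumed rates**

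Inputs:
- n = 192 per arm, from the 385 to be randomised in Section 9.1 (385 / 2 = 192.5, rounded down).
- Two-sided 5% level, from Section 9.2.
- Assumed: true event rates p_P on placebo and p_F on furosemide.
- Assumed: a share a of events judged drug-related, equal in both arms because assessors are blinded.

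The counted rates are a·p_P and a·p_F, so:
- risk difference = a·(p_F − p_P), which shrinks in proportion to a;
- relative risk = a·p_F / (a·p_P) = p_F / p_P, unchanged but estimated from fewer events.

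Power = Φ[(d − 1.96·SE0) / SE1], where d is the difference in counted rates, p̄ is their mean, SE0 = √[2·p̄(1 − p̄)/n], and SE1 = √[(p1(1 − p1) + p2(1 − p2))/n], with p1 and p2 the counted rates.

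All events, 10% v 20%: p̄ = 0.15, SE0 = 0.0364, SE1 = 0.0361. (0.10 − 0.0714)/0.0361 = 0.79, and Φ(0.79) gives power 0.79.

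Half of events kept, 5% v 10%: p̄ = 0.075, SE0 = 0.0269, SE1 = 0.0268. (0.05 − 0.0527)/0.0268 = −0.10, and Φ(−0.10) gives power 0.46.

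Power over a range of assumptions:

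| Share kept (a) | Risk difference | 5% v 15% | 10% v 20% | 20% v 30% |
|---|---|---|---|---|
| 1.0 (all events) | 10 points | 0.91 | 0.79 | 0.62 |
| 0.9 | 9 points | 0.87 | 0.73 | 0.56 |
| 0.7 | 7 points | 0.77 | 0.61 | 0.44 |
| 0.5 | 5 points | 0.61 | 0.46 | 0.32 |
| 0.3 | 3 points | 0.41 | 0.29 | 0.20 |

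A lenient filter costs little and a strict one costs a good deal. The documents do not indicate where a would lie.

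**The case against.** The strongest reply is that the endpoint means reading (b). The protocol lists furosemide's effects and partly puts them to use in Section 4.2, and Section 9.2 compares categorical outcomes between groups. On that reading nothing is filtered. This stands as an equally open interpretation. It does not remove the point, because the endpoint does not say so, and writing reading (b) down is part of the fix.

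Several stronger conclusions are tempting, and the documents do not support them:

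- **That the 7.3 scale determines the endpoint and events graded unrelated are dropped.** No section links 7.3 to 2.3.2.6 or drops graded events from analysis. The unrelated grade is also reserved for events that clearly have nothing to do with treatment. A listed effect such as dizziness, assessed blind, would more naturally be graded possible.
- **That attribution replaces the randomised comparison.** Whatever is counted would still be compared between randomised arms. An equal filter dilutes the risk difference without displacing the comparison.
- **That diuresis would reveal the arm and bias attribution.** The documents give no evidence of this.
- **That kidney injury would be lost.** It is a named component of endpoint 2.3.2.5, which asks for no attribution to furosemide, although that endpoint is confined to complications in hospital related to hypertensive disease.

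Other safeguards are also free of drug attribution: the monitoring board's composite in Section 5.7 and the neonatal admission data in Section 3.3. Neither reports the listed maternal side effects as a named outcome. Finally, no power was planned for this endpoint, so no planned power is lost.

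**Conclusion.** The point holds as a matter of definition. Endpoint 2.3.2.6 is worded by cause, lacks an event list, window and counting rule, and is not backed by any commitment to compare all adverse events by arm. Read literally, it depends on a blinded causality judgement, a poorer measure of harm than counts by arm regardless of cause.

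Its size cannot be fixed from the documents. Under reading (b) there is no dilution. Under reading (a), if attribution is equal in the two arms, the risk difference shrinks by the share of events not attributed. Across the assumed rates, keeping half of events takes power from between 0.62 and 0.91 down to between 0.32 and 0.61. These figures illustrate the mechanism and do not forecast the trial. Nothing here shows that harms would disappear from the trial or that the comparison would be biased. This is a free improvement: a clearer endpoint built on events the protocol already defines and follows, with no effect on the primary analysis.

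**What to change.** Restate 2.3.2.6 as the incidence, by randomised arm and regardless of attribution, of:

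1. each effect already listed in Sections 4.2 and 8.1;
2. any adverse event;
3. any serious adverse event.

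Count each woman once per event type, among those who took at least one dose. State the window, for example from first dose to the end of the 10-day follow-up after discharge for adverse events, and to the 30 days after last dose in Section 7.4.1 for serious events. Report risk differences with 95% confidence intervals, alongside the relative risks that Section 9.2 already promises. Use the 7.3 grades only for expedited reporting or as a supplementary display.

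The cost is the endpoint wording, a sentence in Section 9.2 and one table. Treatment, blinding and sample size do not change.

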3 PATIENT ELIGIBILITY

Subjects must meet all of the inclusion and exclusion criteria to be enrolled to the study. Study treatment may not begin until a subject is consented and randomized.

3.1 Inclusion Criteria

- **3.1.1** Hypertensive disorder of pregnancy diagnosed antepartum or intrapartum
 - Patients with diagnosis of preeclampsia with severe features, superimposed preeclampsia and gestational hypertension as diagnosed per ACOG guidelines¹⁰
 - Gestational hypertension
 - Two blood pressures at least 4 hours apart ≥ 140/90 with no proteinuria or other laboratory abnormalities (detailed below)
 - Pre-eclampsia with severe features and superimposed pre-eclampsia (any of the findings below)
 - Two blood pressures at least 4 hours apart ≥ 160/110 (unless patient given antihypertensive therapy before this time)
 - Thrombocytopenia (platelets <100,000/microliter)
 - Liver enzymes at least twice the normal concentration, and/or severe right upper quadrant/ epigastric pain
 - Serum creatinine > 1.1 mg/dL or a doubling of baseline serum creatinine
 - Pulmonary edema
 - New-onset cerebral or visual disturbances (headache, blurry vision)

- 3.1.2 New diagnosis of HDP within 1 day from delivery
- 3.1.3 Postpartum, delivery ≥ 20 weeks EGA
- **3.1.4** Age ≥18 years old
- **3.1.5** Have a phone with texting service and be willing to enroll in HUP's established postpartum hypertension texting program, HeartSafe Motherhood
- **3.1.6** Ability to understand and the willingness to sign a written informed consent and comply with study procedures

3.2 Exclusion Criteria

- **3.2.1** History of allergic reaction to furosemide
- 3.2.2 High risk comorbidities for which treatment may be indicated or contraindicated: class C or higher diabetes mellitus, chronic kidney disease or baseline creatinine >1.2, cardiac disorders including cardiomyopathy, congenital heart disease, angina or coronary heart disease, rheumatic disease (lupus), sickle cell disease
- 3.2.3 Baseline labs with K <3
- 3.2.4 Use of furosemide or other diuretics antepartum or intrapartum
- **3.2.5** Use of ototoxic agents including aminoglycosides (ie, Gentamicin for >1 dose), cephalosporins (ie Ancef >1 dose),
- **3.2.6** Patient unstable for protocol per investigator's judgement

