4.3 Concomitant Medications/Treatments

To maintain adequate blood pressure control postpartum (goal SBP < 150 mmHg and DBP < 100 mmHg) additional antihypertensive medications may be necessary, and should be used at any time in the postpartum period regardless of enrollment time and first study drug administration:

- 1) Any patient with persistent postpartum blood pressures, ≥150 mmHg systolic and/or ≥100 mmHg diastolic, will be started on 5 mg of amlodipine PO regardless of study arm or whether they are already taking another antihypertensive maintained from their antepartum period.
- 2) Any patient with persistent postpartum blood pressures, ≥160 mmHg systolic and/or 100 mmHg diastolic, will be started on 10 mg of amlodipine PO.
- 3) If blood pressures are still higher than the stated goal above, providers should utilize additional non-diuretic antihypertensive* medications known to be effective in managing elevated peripartum blood pressures.

*Providers will be asked to use non-diuretic medications first, however, if deemed medically necessary, furosemide will be allowed any time in the postpartum period. All uses of diuretic use for medically necessary reasons after enrollment of patient into the trial will be noted.

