5 STUDY PROCEDURES

5.1 Screening for Recruitment and Recruitment Process

The labor and delivery board and patient list will be screened daily to identify eligible patients. Women identified as having a hypertensive disorder of pregnancy will be invited to participate in the study and written informed consent will be obtained from those who choose to participate in the postpartum period. All screening procedures must be performed within 24 hours of delivery. The screening procedures include:

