5.3 Procedures During Treatment

After enrollment and consent, a specific order will be placed in the electronic medical record for this study's purposes. This order will alert IDS that a patient has been enrolled and the patient will be randomized accordingly. After randomization, IDS will send to the floor either 5 doses of placebo or furosemide clearly marked for the specific patient. A research coordinator will be present at this time and ensure that there are 5 doses of furosemide/placebo and that the patient's nurse is aware that the patient is enrolled in the study. The research coordinator will also ensure that the medication order is given by postpartum day 1 and ensures that the first pill is given after 6 hours from delivery. Patients in the furosemide arm will be assigned to receive oral furosemide 20 mg/day for a total of 5 consecutive days during hospitalization and after discharge. This dose of furosemide is based on prior studies,3 which have shown it to be safe with breast feeding. For those randomized to the placebo group, they will be given placebo pills for a total of 5 consecutive days. The time of initiation of first pill given will be recorded by the research coordinator. Each time a pill is given in the hospital, it will be accounted for in the medical administration record (MAR) in the EMR. Pills should be given approximately 24 hours apart, and the Epic order placed after enrollment will have this distinction.

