Patients in both groups will undergo similar postpartum surveillance, including blood pressure and pulse assessment every 4 hours and urinary output measurements while hospitalized. Proper treatment for elevated blood pressures will be initiated immediately as soon as the elevated blood pressures are recognized, and will not be delayed for any study purposes including study drug administration. For this study, antihypertensive therapy will be initiated for persistently elevated postpartum blood pressures (BP) of ≥ 150 systolic or >100 mg Hg diastolic with 5 mg of amlodipine PO. Persistent severe range blood pressures (BP >160 mm Hg systolic or >110 mm Hg diastolic) will be treated with IV antihypertensives if needed, as well as 10 mg of amlodipine PO. If further antihypertensive medications are needed to maintain blood pressures <150/100, these will be per the discretion of the clinical staff in both arms. All physicians and clinical staff in Labor and Delivery as well the postpartum unit will be educated extensively to avoid diuretic antihypertensive medications unless deemed medically necessary. Furthermore, diagnostic and laboratory tests will be per the discretion of the clinical staff in both arms as well. Routinely, all patients undergoing cesarean section remain hospitalized for at least 3 days and all patients with preeclampsia with severe features are kept in the hospital for 3 days (per the recommendations of the ACOG Task Force on Hypertension in Pregnancy). 10 All patients will be followed at for 10 days after discharge as detailed below. Being enrolled in the study will not change the patient's clinical care at any time. Physicians, staff, and patients will be blinded to the intervention administered, unless a break in blinding is required for medical intervention of adverse effects.

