5.7 Protections Against Physical Risk

There is minimal risk to use of furosemide in the postpartum period. Furosemide is a commonly used drug in postpartum period and prior studies have not shown any adverse effects in this patient population. At the Hospital of University of Pennsylvania, furosemide has been used frequently as part of a postpartum hypertension protocol. A DSMB comprised of individuals who are not investigators on the trial will be utilized to monitor for adverse outcomes. A list of mandatory events that should be reported to the DSMB within 24 hours of occurrence will be supplied to all clinicians and research coordinators managing trial patients. The DSMB will stop the trial if there is a 20% increase in the rates of adverse outcomes (a composite outcome). The DSMB will review the data every 6 months. Also all serious adverse effect will be recorded and reported to the institutional review board.

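### Exclusion 3.2.4 stops at delivery, so a woman given open-label furosemide between delivery and randomisation stays eligible; a minor gap with a cheap fix

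*Combined protocol and SAP*

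**What the plan says.** The diuretic criterion in section 3.2 (item 3.2.4) reads "Use of furosemide or other diuretics antepartum or intrapartum". No other item in 3.2 mentions diuretics; 3.2.6 leaves room for the investigator to exclude a woman, but only for instability.

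The steps that lead to randomisation fall after that window. Under section 5.1, "written informed consent will be obtained from those who choose to participate in the postpartum period", and "All screening procedures must be performed within 24 hours of delivery". The schedule in 5.5 marks randomisation at enrolment and within one day of delivery. Section 5.3 has the coordinator ensure that "the medication order is given by postpartum day 1 and ensures that the first pill is given after 6 hours from delivery".

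On open-label use, the footnote to section 4.3 asks providers to use non-diuretic agents first, then adds that "if deemed medically necessary, furosemide will be allowed any time in the postpartum period". It continues: "All uses of diuretic use for medically necessary reasons after enrollment of patient into the trial will be noted". Section 5.3 says that staff on labor and delivery and the postpartum unit will be "educated extensively to avoid diuretic antihypertensive medications unless deemed medically necessary", and sections 3.4, 4.3 and 5.3 name amlodipine as the first agent. Section 5.7, in arguing that the drug is safe, says of this hospital that "furosemide has been used frequently as part of a postpartum hypertension protocol".

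**The concern.** The evident purpose of 3.2.4 is to randomise women who have not recently had a diuretic, yet it leaves out the hours directly before randomisation. A diuretic taken at some point in pregnancy disqualifies a woman; the study drug itself, given a few hours before she is randomised, does not.

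Exposure in that gap is plausible. The site reports frequent postpartum use, section 4.3 permits medically necessary use, and pulmonary edema is one of the qualifying features in 3.1.1.

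If exposed women enter, some placebo women will have received the active drug and some furosemide women will have received extra. The first narrows the contrast on the primary composite and the blood pressure endpoints; the second adds exposure in the active arm. Neither would be easy to see in the analysis. Section 4.3 commits to noting diuretic use only after enrolment, the composite in 2.3.1.1 counts antihypertensives only after randomisation, the stratification in 5.2 is by severe features alone, and section 9.2 has no analysis for earlier diuretic use.

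**Working it through.** **Is the gap closed elsewhere?**

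| Step | Section | Timing or effect |
|---|---|---|
| Diuretic exclusion | 3.2.4 | ends at delivery |
| Consent | 5.1 | postpartum |
| Screening | 5.1 | up to 24 hours after delivery |
| Randomisation | 5.5 | up to one day after delivery |
| First study dose | 5.3 | more than 6 hours after delivery |
| Medication review | 5.1.5 | at screening; no eligibility consequence |
| Commitment to note diuretic use | 4.3 | from enrolment |

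The interval from delivery to randomisation has no diuretic criterion.

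**Planned effect.** Section 9.1 gives a control rate of 45.6% and a 40% reduction, read here as relative:
- furosemide rate: 45.6% × 0.60 = 27.36%
- difference: 45.6 − 27.36 = 18.24 points.

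**Planned sample size.** The total follows from 175 per arm: 2 × 175 × 1.10 = 385. The 175 itself does not follow from the stated inputs. The usual two-proportion formula (two-sided 5%, 80% power) gives 109 per arm, or 119 with continuity correction. That is a separate matter, but it bears on how the power figures below are read.

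**Upper-bound dilution.** Let f be the share of women exposed before randomisation. The documents give no value, so 5%, 10% and 20% are assumptions. Suppose exposed placebo women get the full drug effect and the furosemide arm is unchanged:
- placebo rate = (1 − f) × 45.6% + f × 27.36%
- difference = (1 − f) × 18.24 points.

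Power at 175 per arm, without continuity correction, is Φ[(d − 1.96 × SE₀)/SE₁], where d is the difference, SE₀ uses the pooled variance and SE₁ the unpooled variance.

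| f (assumed) | Placebo rate | Difference (points) | Power at 175 per arm |
|---|---|---|---|
| 0 | 45.6% | 18.2 | 94.7% |
| 5% | 44.7% | 17.3 | 92.5% |
| 10% | 43.8% | 16.4 | 89.7% |
| 20% | 42.0% | 14.6 | 82.1% |

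Power remains above 80% at these shares because 175 exceeds the 109 that the stated inputs require. That margin depends on the 40% effect. With a 30% relative reduction, power at 175 per arm would be 75.0% with nobody exposed, and 70.7%, 66.1% and 56.2% at the three shares.

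**Why this is an upper bound.** Section 1.2 gives furosemide a half-life of 0.5–2 hours and an oral effect of 6–8 hours. Section 1.3 places the blood pressure rise on days 3–6, and the blood pressure part of the primary endpoint is read at day 7. After one early open-label dose, the arms still differ by five daily doses of furosemide against none.

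**The case against.** The case against accepts the wording gap but holds that it may have almost no effect, and most of that stands.

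- **Frequency.** The section 5.7 statement describes past practice, offered to support safety. It gives no rate and does not place use in the first day. Staff education, the request to use non-diuretics first, and amlodipine as first agent all push use down. Exposure before randomisation could be close to zero.
- **Contrast.** A reader might infer that exposed women are already on continuing open-label furosemide, so that randomisation offers them little or no contrast. The documents do not support this. Contrast would vanish only if open-label use went on after randomisation, and section 4.3 already allows and records that.
- **Permission.** A reader might also infer that 4.3 permits furosemide irrespective of enrolment time. That phrase governs additional antihypertensives in general; furosemide comes in only through the footnote, with its medical-necessity condition.
- **Bias.** Exposed women may well be sicker, but that does not create imbalance. Allocation is randomised, blocked and stratified by severe features.
- **Detection.** The 5.1.5 review should already bring such use to light.
- **Cost.** If few women are exposed, dilution is trivial; if many are, excluding them costs recruitment at a single centre.

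These points bear on size. They do not close the gap: the education and first-line rules leave room for clinical use, and the 5.1.5 review has no criterion to apply.

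**Conclusion.** The gap holds as a matter of text: the diuretic exclusion omits the interval between delivery and randomisation, and nothing else in the plan supplies it. The consequence is possible dilution and some added exposure in the furosemide arm.

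Severity is minor. The size is unknown and probably small. The figures of 17.3, 16.4 and 14.6 points rest on assumed shares and on zero contrast in exposed women, which overstates the effect of one early dose. On the plan's stated inputs these shares do not take power below 80%, so the documents do not support a conclusion that this gap alone leaves the trial underpowered. That reassurance assumes the 40% relative reduction. Confidence is high on the wording gap and low on any particular size of effect.

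**What to change.** Extend 3.2.4 to cover use *antepartum, intrapartum, or postpartum before randomization*. Make it an explicit check in the 5.1.5 medication review, against the medication administration record, and change 4.3 so that diuretic use is recorded from delivery.

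Because the criterion acts before randomisation, it leaves the intention-to-treat analysis intact. It does not alter what clinicians may give, and it does not address open-label use after randomisation.

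The cost is a one-line eligibility amendment and one record check per woman, and a few screened women become ineligible. If the sponsor prefers to keep such women in the trial, the minimum is to record earlier diuretic use as a baseline variable and prespecify a sensitivity analysis that leaves them out.
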